2.5 Out of Window and Unscheduled Visits

All scheduled assessments after first administration of randomized study product will be used. The protocol defined windows for scheduled visits will not be used in the analyses by visit. Data will be assigned to the scheduled visit closer in time to the scheduled visit. Unscheduled visit data will only be used in an analysis if there is no other available data closer in time to a scheduled visit. Post first dose unscheduled assessments will be taken into account for worst-case determination as applicable. All unscheduled visit data will be included in data listings.

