2.6.4 Full Treated Set

The full treated set (FTS) will include all enrolled patients who received treatment of study drug through Visit 6.

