5 ANALYSIS OF EFFICACY

5.1 Primary Efficacy Variable

The primary efficacy variable is the achievement of epithelial healing at Visit 6/Week 8, which is defined as Grade 1 or absence of staining (Grade 0) in the central qualifying zone of study eye via FCS (per NEI scale). The primary efficacy variable will be summarized as a binary goal attainment variable (Yes/No).

The primary analysis will be based on observed cases (i.e. no missing data imputation). As a sensitivity analysis, the last post baseline observation prior to Week 8 will be carried forward for imputing missing data at Week 8. In addition the worst post baseline observation prior to Week 8 will be carried forward for imputing missing data at Week 8 and patients who took any rescue medication prior to Week 8 will be considered as a treatment failure (not epithelial healed) at Week 8.

All summaries and analyses for the primary efficacy variable will be presented for both FAS and FTS populations.

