5.2 Secondary Efficacy Variables

All the analyses of secondary efficacy variables will be performed based on the observed cases in the FAS population. No missing data imputation will be considered.

• Percentage of patients who experienced epithelial healing at 4 weeks

The patients who experienced epithelial healing at Visit 4/Week 4 will be determined for study eye similarly as the primary efficacy variable. It will be summarized as a binary goal attainment variable (Yes/No).

• Percentage of patients who achieved epithelial healing at Week 8 and remained healed throughout the follow-up period

The patients who achieved epithelial healing at Week 8 and remained healed throughout the follow-up period will be determined for study eye at Visit 7/Week 32 similarly as the primary efficacy variable. It will be summarized as a binary goal attainment variable (Yes/No) based on the subset of patients who achieved epithelial healing at Week 8, as well as based on the FTS.

• Percentage of patients who experienced complete healing at Week 4 and 8

The patients who experienced complete healing at Week 4 and 8 will be determined for study eye by the investigator and recorded on eCRF. The complete healing is defined as Grade \leq 1 in the central qualifying zone of study eye via FCS (per NEI scale) and no persistent staining in the non-qualifying zones (excluding the superior zone) defined as the absence (Grade 0) of pathological staining via corneal photography. It will be summarized as a binary goal attainment variable (Yes/No).

• Percentage of patients who achieved complete healing at Week 8 and remained completely healed throughout the follow-up period

The patients who achieved complete healing at Week 8 and remained healed throughout the follow-up period will be determined for study eye at Visit 7/Week 32 by the investigator and recorded on eCRF. It will be summarized as a binary goal attainment variable (Yes/No) based on the subset of patients who achieved complete healing at Week 8, as well as based on the FTS.

• Mean change in corneal sensitivity from baseline at 4, 8, and 32 weeks

The corneal sensitivity (cm) in the NEI zone of the study eye as measured by the Cochet-Bonnet aesthesiometer will be summarized as a continuous variable.

• Percentage of patients that achieve an improvement in corneal sensitivity at 4, 8, and 32 weeks

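### Week 8 healers discontinued for deterioration early in follow-up have no stated outcome; on observed cases at Week 32 they are missing rather than failures, which can inflate the remained-healed rate

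*SAP*

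**What the plan says.** SAP 5.2 sets one missing-data rule for all secondary variables: the analyses "will be performed based on the observed cases in the FAS population. No missing data imputation will be considered". Remaining healed throughout follow-up "will be determined for study eye at Visit 7/Week 32 similarly as the primary efficacy variable", and is reported as Yes/No "based on the subset of patients who achieved epithelial healing at Week 8, as well as based on the FTS". The complete-healing version has the same structure. The FTS is defined in SAP 2.6.4 as "all enrolled patients who received treatment of study drug through Visit 6", and both durability tables (14.2.1.2 and 14.2.2.2) list that set.

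Protocol 3.3 discontinues a patient whose study eye meets the deterioration criteria during follow-up. Protocol 6.2 has the Visit 6 procedures done at exit and ends follow-up there. The Schedule of Evaluations has no visit between Week 8 (Day 56) and Week 32 (Day 224), so an earlier relapse comes to light only at an unscheduled visit.

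SAP 2.5 governs where such an examination goes: "Data will be assigned to the scheduled visit closer in time to the scheduled visit", and "Unscheduled visit data will only be used in an analysis if there is no other available data closer in time to a scheduled visit". It adds that "Post first dose unscheduled assessments will be taken into account for worst-case determination as applicable", without naming any analysis. The only imputation and failure rules are in SAP 5.1 and concern the primary variable, for example that "the worst post baseline observation prior to Week 8 will be carried forward for imputing missing data at Week 8". Protocol 9.3.4 left the imputation details to the SAP.

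**The concern.** Staying healed is the first secondary objective, and the endpoint is worded as holding throughout follow-up. The plan removes deteriorating eyes from the study and then analyses only those with a Week 32 value. Missingness is therefore caused by the outcome. The relapses most likely to force an early exit are the severe ones (PED, melting, perforation), so they are the ones most likely to disappear from the rate. The same relapse counts against durability if it is first seen at Week 32, but may count for nothing if it is found and acted on earlier. In a single-arm study with no hypothesis test, the percentage and its exact interval are the result, and here both depend on a choice the SAP does not state.

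**Working it through.** **The plan's own figure.** Protocol 9.1 gives lower 95% limits of 40% and 54% for n = 35 at healing rates of 58% and 72%. The Clopper-Pearson lower limit, the 0.025 quantile of Beta(x, n − x + 1) with x = 0.58 × 35 = 20.3 and x = 0.72 × 35 = 25.2, is 40.2% and 54.3%. The figures reproduce, so the same exact method (named in SAP 5.4) is used below.

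**Where an early exit examination lands.** The midpoint of Days 56 and 224 is (56 + 224)/2 = 140, or Week 20. This cut-off is inferred from the nearest-visit rule; neither document states it. An exit before about Day 140 is nearer to Week 8. The actual Visit 6 is closer still to Day 56, so the exit examination is not used, and nothing is left for Week 32. An exit after about Day 140 maps to Week 32 and can be scored as not healed. The gap is therefore confined to early follow-up.

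**Effect on the rate.** Inputs: Week 8 healers H = 0.72 × 35 = 25.2, taken as 25; s = number who truly stay healed (assumed 20 or 15); k = early relapsers lost (assumed 0 to 3). The documents give neither s nor k. Counting lost relapsers as failures gives s/25. Observed cases give s/(25 − k), which is larger whenever k > 0 and s > 0.

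| k | s = 20, healed subset (95% CI) | s = 15, healed subset (95% CI) | s = 20, FTS with missing dropped, 20/(35 − k) (95% CI) |
|---|---|---|---|
| 0 | 20/25 = 80.0% (59.3–93.2) | 15/25 = 60.0% (38.7–78.9) | 20/35 = 57.1% (39.4–73.7) |
| 1 | 20/24 = 83.3% (62.6–95.3) | 15/24 = 62.5% (40.6–81.2) | 20/34 = 58.8% (40.7–75.4) |
| 2 | 20/23 = 87.0% (66.4–97.2) | 15/23 = 65.2% (42.7–83.6) | 20/33 = 60.6% (42.1–77.1) |
| 3 | 20/22 = 90.9% (70.8–98.9) | 15/22 = 68.2% (45.1–86.1) | 20/32 = 62.5% (43.7–78.9) |

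The steps in the healed subset are +3.3, +3.6 and +4.0 points for s = 20, and +2.5, +2.7 and +3.0 for s = 15. The FTS column keeps the 10 Week 8 non-healers as No. If a missing Week 32 value is also scored No, the FTS rate stays at 57.1% for every k.

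**Exits that are not central relapses.** Suppose 1, 2 or 3 of the 20 leave for another deterioration reason with central grade 1 or less. Scored as failures they give 19/25 = 76.0%, 18/25 = 72.0% or 17/25 = 68.0%. With the last central grade carried forward the rate is 80.0%.

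**The case against.** The strongest reply is that the durability bullets override the general sentence. They name two bases, Week 8 healers and the FTS, that are fixed by Week 8, and a Yes/No variable that could be read as No unless healing at Week 32 is shown. On that reading the FTS bias is zero. SAP 2.5 can also be read from the Week 32 side: for a patient with no Visit 7, the exit examination is the nearest value to Day 224 and would be used whatever its date. The worst-case sentence might cover it too. These readings are possible, but no text states them, and the observed-case and nearest-visit sentences point the other way. Protocol 6.1.6 gives the premature discontinuation visit its own label, but as Visit 6, which gives it no claim to be a Week 32 value.

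The trigger is narrow, and this stands. Relapse to central Grade 2 is not itself a listed criterion, so such a patient would generally stay in and be counted at Week 32. Protocol 6.2 says patients may, rather than must, be discontinued, and it ties unchanged Grade 3 to the end of eight weeks of treatment. PED, melting and perforation, however, are triggers in both 3.3 and 6.2.

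The upward direction applies to lost relapsers, not to every exit. Infection, visual acuity loss, surgery or progression in other zones can occur with the centre still healed. Losing one patient who would have stayed healed gives 19/24 = 79.2%, slightly below 80.0%.

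The losses would also be partly visible, through visit completion, discontinuation reasons and the staining listing, and SAP 2.10 calls all efficacy analyses exploratory. A reader could rebuild some of the rate, but the reported percentage and interval would still rest on an unstated choice.

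**Conclusion.** The concern holds. Followed as written, the observed-case and nearest-visit rules can drop a documented early relapse from an endpoint defined over the whole follow-up, and for such relapses the effect is only upward. Its size cannot be known from the documents. Under the assumptions above it is about 2.5 to 4 points per lost relapser in the healed subset, and under 2 points in the FTS if missing values are dropped. One loss is small against an interval of 59.3 to 93.2%; three would turn 80.0% into 90.9%. The conclusion rests on deteriorating healers being removed before about Day 140 and on reading SAP 2.5 as assigning their exit examination to Week 8. The complete-healing durability endpoint has the same gap.

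**What to change.** Add a short rule to SAP 5.2:

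- Keep all Week 8 healers in the healed-subset denominator, and all FTS patients in the FTS denominator with Week 8 non-healers as No.
- Count a Week 8 healer as not having remained healed if any examination after Week 8, including an unscheduled or exit visit, shows central staining of Grade 2 or more in the study eye, or if the patient is discontinued for PED, melting or perforation, whether or not a Week 32 value exists.
- Some healers will leave for other deterioration reasons (infection, loss of more than 10 letters, ocular surgery, non-qualifying-zone progression) with central grade 1 or less, or for unrelated reasons without a Week 32 value. For them, report epithelial-healing durability twice: as failure, and with the last central grade carried forward. List them by reason.
- Show observed cases as a sensitivity analysis.
- Apply the same rule to complete-healing durability, using the complete-healing definition.

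The cost is one paragraph in the SAP and extra rows in Tables 14.2.1.2 and 14.2.2.2. All the data are already collected, so no visit or protocol amendment is needed. The price is a slightly lower, more conservative durability estimate.

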Appendix 2 Shells for Tables, Listing, and Figures List of tables

| Table Number | Table Title | Analysis Population |
|-----------------|--|------------------------|
| 14.1.1 | Analysis Populations | Screened |
| 14.1.2 | Subject Disposition | Screened |
| 14.1.3 | Visit Participation | Full Analysis Set |
| 14.1.4 | Demographics | Full Analysis Set |
| 14.1.5.1 | Medical History | Full Analysis Set |
| 14.1.5.2 | Ocular History | Full Analysis Set |
| 14.1.6.1.1 | Ocular Prior Medications | Full Analysis Set |
| 14.1.6.1.2 | Non-ocular Prior Medications | Full Analysis Set |
| 14.1.6.2.1 | Ocular Concomitant Medications | Full Analysis Set |
| 14.1.6.2.2 | Non-ocular Concomitant Medications | Full Analysis Set |
| 14.1.7.1 | Treatment Exposure of Study Product | Full Analysis Set |
| 14.1.7.2 | Washout Use of Artificial Tears | Full Analysis Set |
| 14.1.7.3 | Treatment Compliance of Study Product | Full Analysis Set |
| 14.2.1.1.1 | Percentage of Patients who Experienced with Epithelial Healing at 8 weeks | Full Analysis Set |
| 14.2.1.1.2 | Percentage of Patients who Experienced with Epithelial Healing at 8 weeks | Full Treated Set |
| 14.2.1.1.3 | Percentage of Patients who Experienced with Epithelial Healing at 8 weeks - LOCF | Full Analysis Set |
| 14.2.1.1.4 | Percentage of Patients who Experienced with Epithelial Healing at 8 weeks - WOCF | Full Analysis Set |
| 14.2.1.2 | Percentage of Patients who Achieved Epithelial Healing at Week 8 and Remained Healed during Follow-up | Full Treated Set |
| 14.2.1.3 | Percentage of Patients who Experienced with Epithelial Healing at 4 weeks | Full Analysis Set |
| 14.2.2.1 | Percentage of Patients who Experienced with Complete Healing at 8 weeks | Full Analysis Set |
| 14.2.2.2 | Percentage of Patients who Achieved Complete Healing at Week 8 and Remained Healed during Follow-up | Full Treated Set |
| 14.2.2.3 | Percentage of Patients who Experienced with Complete Healing at 4 weeks | Full Analysis Set |
| 14.2.3.1 | Corneal Sensitivity Change from Baseline to Weeks 4, 8, and 32 | Full Analysis Set |
| 14.2.3.2 | Percentage of Patients Improved from Baseline in Corneal Sensitivity at 4, 8 and 32 weeks | Full Analysis Set |
| 14.2.4 | Schirmer I Change from Baseline to Weeks 4, 8, and 32 | Full Analysis Set |
| 14.2.5 | TFBUT Change from Baseline to Weeks 4, 8, and 32 | Full Analysis Set |
| 14.2.6.1 | BCDVA Change from Baseline to Weeks 4, 8, and 32 | Full Analysis Set |

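### Under the observed-case rule, a Week 8 healer who exits before about Day 140 with documented loss of healing can drop out of the healed-subset remained-healed rate

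*SAP*

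**What the plan says.** SAP 5.2 states that secondary efficacy analyses are "performed based on the observed cases in the FAS population. No missing data imputation will be considered". For the epithelial endpoint, Week 8 healers who "remained healed throughout the follow-up period will be determined for study eye at Visit 7/Week 32 similarly as the primary efficacy variable". The rate is to be given "based on the subset of patients who achieved epithelial healing at Week 8, as well as based on the FTS". The complete-healing version has the same structure, with status recorded by the investigator on the eCRF. The FTS is "all enrolled patients who received treatment of study drug through Visit 6" (SAP 2.6.4).

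SAP 2.5 sets aside the protocol visit windows. It says "Data will be assigned to the scheduled visit closer in time to the scheduled visit", and "Unscheduled visit data will only be used in an analysis if there is no other available data closer in time to a scheduled visit". It adds that unscheduled assessments after the first dose feed into worst-case determinations where applicable, without naming an endpoint.

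Protocol 3.3 discontinues patients whose study eye meets Deterioration or No Improvement during follow-up. Protocol 6.2 has them complete the Visit 6 procedures, which include fluorescein staining, and then ends their follow-up. They are not replaced. Protocol 7.1.1 defines the endpoint as staying healed over the whole follow-up period, and Protocol 2.4 uses it to measure how well the effect is preserved.

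SAP Appendix 2 lists two durability tables, 14.2.1.2 ("Percentage of Patients who Achieved Epithelial Healing at Week 8 and Remained Healed during Follow-up") and 14.2.2.2 ("Percentage of Patients who Achieved Complete Healing at Week 8 and Remained Healed during Follow-up"), both under the FTS. No table is listed for the healed subset.

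**The concern.** The endpoint asks whether healing lasted through follow-up, but status is read at one visit, on whoever has a value there. Some of the events that remove a patient before that visit are themselves failures of the endpoint: return to central Grade 3, progression to a PED, or another exit reason accompanied by loss of healing. For those patients the Week 32 value is missing because healing was lost, and leaving them out raises the healed-subset rate.

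The result also depends on the calendar. The same documented relapse can count as a failure at Day 150 and go unused at Day 130.

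SAP 5.1 gives the Week 8 endpoint LOCF, a worst-observation analysis and a rescue-as-failure rule. Week 32 has nothing comparable, although durability belongs to the secondary objective. In a single-arm study without tests, the estimate and its interval are the result.

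**Working it through.** **Inputs.** Planned n = 35 and assumed Week 8 healing of 72% (Protocol 9.1). Visit 6 is Day 56 and Visit 7 is Day 224 (Protocol 2), with no scheduled visit between them. Intervals are Clopper-Pearson (SAP 5.4). The documents give no relapse count, no share of relapses caught before Visit 7 and no exit timing, so all three are assumed below.

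**The plan's own figure.** The Clopper-Pearson lower limit at 72% of 35 (x = 25.2) is 54.3%, and at 58% (x = 20.3) it is 40.2%. These match the stated 54% and 40%. I take 25 healers as the base.

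**Where an exit examination lands.** The midpoint is (56 + 224)/2 = Day 140. Day 139 is 83 days from Week 8 and 85 from Week 32; Day 141 is 85 and 83. Before about Day 140 the examination maps to Week 8. There the patient's actual Visit 6 value is closer to the nominal day, so the exit record is unused and Week 32 stays empty. Days 57 to 139 are 83 of the 168 follow-up days (49.4%, taken as 0.5).

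**Effect on the rate.** Let R be the relapses among 25 healers and d those lost before Week 32. The rate with all relapses counted is (25 − R)/25. The observed-case rate is (25 − R)/(25 − d). With R = 5:

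| d | Observed-case rate | 95% CI |
|---|---|---|
| 0 | 20/25 = 80.0% | 59.3 to 93.2 |
| 1 | 20/24 = 83.3% | 62.6 to 95.3 |
| 2 | 20/23 = 87.0% | 66.4 to 97.2 |

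**Mean bias.** Let c be the share of relapses caught and discontinued, with exits spread evenly over follow-up, so d ~ Binomial(R, 0.5c). For R = 5:

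- c = 10%: P(d = 0, 1, 2, 3) = 0.774, 0.204, 0.021, 0.001. The mean is 0.774 × 80.0 + 0.204 × 83.3 + 0.021 × 87.0 + 0.001 × 90.9 = 80.8%, a bias of +0.8 points.
- c = 25%: 82.1%, or +2.1.
- c = 50%: 84.4%, or +4.4.

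At c = 25% and 50% the bias is +1.0 and +1.9 for R = 2 (92.0% with all counted), and +2.9 and +6.1 for R = 8 (68.0%).

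**Opposite direction.** Suppose all 5 relapses are seen at Visit 7 and 2 healers leave with the central zone still healed. The observed-case rate is 18/23 = 78.3%, against 80.0% had those 2 stayed and remained healed.

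**FTS version, R = 5.** With a fixed denominator, 20/35 = 57.1%. If the observed-case sentence governs and d = 2, 20/33 = 60.6%.

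**The case against.** The strongest reply is that the SAP can be read to count these patients. Three pieces of text support it.

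- The worst-case sentence in SAP 2.5 could apply to an endpoint about remaining healed over a period.
- The sentence "Unscheduled visit data will only be used in an analysis if there is no other available data closer in time to a scheduled visit" could be applied to the empty Week 32 slot. The exit record is then the closest available one, so it fills the slot and scores as a failure.
- The durability bullets name their own denominators, which could override the general observed-case sentence and keep every Week 8 healer in.

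These readings are possible, and they are why the finding says *can*. None is stated for this endpoint. The nearest-visit sentence and the observed-case sentence both point the other way.

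The second reply is that few patients are affected. That largely stands. The listed staining criterion for exit is Grade 3, so a central relapse to Grade 2 alone does not meet it; without another exit reason that patient stays in and is counted at Visit 7. Unscheduled visits are discretionary, so many relapses would first be seen at Visit 7. Exits after about Day 140 can map to Week 32.

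Third, both listed durability tables use the FTS, and the detailed shells are a separate document that may define the rows. With a fixed FTS denominator there is no upward bias. But SAP 5.2 also commits to the healed-subset rate, and it does not say which denominator rule prevails for either version.

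Finally, SAP 2.10 makes all efficacy analyses exploratory, and discontinuation reasons and staining are reported. A reader could see the exits, but would be given no corrected rate.

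**Conclusion.** The gap is real but limited. On the nearest-visit reading of SAP 2.5, combined with the observed-case rule in SAP 5.2, a healer with documented loss of healing before about Day 140 can be removed from the healed-subset rate instead of counted as a failure. Confidence is medium, because other SAP text leaves room to count that patient.

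On assumed inputs (25 healers, 5 relapses, evenly spread exits, 10% to 50% of relapses caught and discontinued) the mean upward bias is about +0.8 to +4.4 points. The interval for 20/25 is about 34 points wide. Larger effects need most relapses to be caught and withdrawn early, and nothing in the documents supports that.

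A reader might infer three stronger things that the documents do not support:

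- **That every deterioration exit is a hidden failure.** Infection, acuity loss, surgery or non-qualifying-zone progression with the central zone still at Grade 0 or 1 is missing data for the epithelial endpoint, and can bias the rate downward.
- **That the listed durability tables are necessarily inflated.** They are FTS tables, and a fixed denominator removes the upward bias.
- **That a conclusion of the trial is invalidated.** The endpoint is descriptive and no test depends on it.

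**What to change.** In SAP 5.2, for both durability endpoints:

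1. Count as not remained healed any Week 8 healer with documented loss of the relevant definition (epithelial or complete) at an exit or unscheduled visit, or discontinued for progression to a PED, melting or perforation, whatever visit the record maps to under SAP 2.5.
2. Fix the denominators as all Week 8 healers and all FTS patients, with patients not healed at Week 8 counted as No in the FTS version. Show healers with neither a Week 32 value nor documented loss in a separate unknown row.
3. Add one sensitivity analysis that counts a missing Week 32 assessment as not remained healed, and keep observed cases as supportive.

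The cost is a few SAP sentences, some derivation code and possibly a lower reported durability rate. No new assessment is needed: staining at exit is part of the Visit 6 procedures, the termination reason goes on the CRF, and SAP 2.5 already lists unscheduled data. The eCRF is not among the documents, so its fields should be confirmed first.

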6.2. EARLY WITHDRAWAL FROM STUDY

A premature discontinuation will occur when a patient who signed the ICF ceases participation in the study, regardless of circumstances, before the completion of the study protocol procedures. Patients can be prematurely discontinued from the study for one of the following reasons:

- Progression from Stage 1 to Stage 2 or Stage 3 NK, or corneal melting/perforation
- At the PI discretion patient is considered to be a non-responder (no improvement from baseline).
- In the qualifying/Study Eye, the FCS is unchanged (Grade=3) from baseline after 8 weeks of treatment in the qualifying NEI zone or there is an increase in FCS ≥1 within a non-qualifying NEI zone in the same eye.
- Decrease in BCDVA by >10 ETDRS letters
- Onset of infection (bacterial or viral)
- Protocol violation, including lack of compliance defined as <80% of doses taken based on diary documentation between treatment clinic visits.
- Withdrawal of consent
- Lost to follow-up during the treatment period (Every effort must be made to contact the patient; a registered letter must be sent)
- Study terminated by the Sponsor
- Other reasons, such as administrative reasons or pregnancy
- Development of AE or unacceptable toxicity per the investigator's discretion, precluding further therapy with the study drug.
- Severe protocol violations, such as an incorrect treatment administration, or a concomitant use of not permitted medications. Before removal, these cases should first be discussed with Dompé.

The reasons for premature discontinuation from the study will be reflected on the Study Termination Record of the CRF. For patients who prematurely discontinue, Visit 6 procedures will be completed, and these patients will be considered off study and will no longer be followed.

For patients that discontinue prematurely, the investigator should refer patients for further treatment as appropriate.

Replacement Procedures

Patients in this study who prematurely discontinue before completion of 8 weeks of treatment with OxervateTM will be replaced. Patients prematurely discontinuing during follow up treatment will not be replaced.

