9.2. PATIENT POPULATION

Screened Population

The Screened Population will consist of all patients who attended Screening, signed the ICF, and were assigned a PID number.

Analysis Sets

Full Analysis Set: consist of all patients who receive at least one dose of study drug.

Full Treated Set: consist of all patients who receive all 8 weeks of treatment.

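### The durable-healing rates have no all-treated denominator, and no rule counts known failures without a Week 32 visit as not durably healed

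*SAP*

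**What the plan says.** **Denominators.** SAP 5.2 opens by placing all secondary variables on observed cases in the FAS, without imputation. Its endpoint-specific text then names two other denominators. Durable epithelial healing is reported "based on the subset of patients who achieved epithelial healing at Week 8, as well as based on the FTS", and durable complete healing "based on the subset of patients who achieved complete healing at Week 8, as well as based on the FTS". In SAP Appendix 2, Table 14.2.1.2 ("Percentage of Patients who Achieved Epithelial Healing at Week 8 and Remained Healed during Follow-up") and its complete-healing counterpart, Table 14.2.2.2, are listed for the FTS only. SAP 5.4 says that efficacy results are tabulated on both sets where appropriate.

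**The FTS.** Protocol 9.2 says that it will "consist of all patients who receive all 8 weeks of treatment". SAP 2.6.4 says: "The full treated set (FTS) will include all enrolled patients who received treatment of study drug through Visit 6". Protocol 6.1.6 makes Visit 6 both the end-of-treatment visit and the premature discontinuation visit.

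**Early stops.** Protocol 6.2 replaces patients "who prematurely discontinue before completion of 8 weeks of treatment with" the study product, whatever the reason. After Visit 6 procedures they are off study. The listed reasons include progression to Stage 2 or 3 and adverse events that preclude therapy, with no time point. Another reason, also without a time point, reads "At the PI discretion patient is considered to be a non-responder (no improvement from baseline". The next bullet applies when "the FCS is unchanged (Grade=3) from baseline after 8 weeks of treatment in the qualifying NEI zone". Protocol 3.3 applies its deterioration or no-improvement definition at Week 8 and during follow-up, and discontinues patients who meet it.

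**The concern.** Durable healing is a stated secondary objective. The trial has no control arm and no hypothesis test, so the reported percentage and its interval are the result, and the denominator determines what that percentage means.

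A patient who progresses or is judged a non-responder before Week 8 cannot have healed at Week 8 and stayed healed. On the completer reading of the FTS, that patient is in neither planned denominator, and a replacement takes the place. The durable rate then describes patients selected for having completed treatment, whereas the Study Rationale (Protocol 2.4) speaks of the percentage of treated patients who remain healed.

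A second gap arises after Week 8. A healer who deteriorates in follow-up is discontinued and may have no Visit 7 value. Under observed cases, the most direct kind of durability failure can then drop out of the calculation.

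**Working it through.** **Step 1. The plan's own figure.** Protocol 9.1 states lower 95% limits of 40% and 54% for healing rates of 58% and 72% with 35 evaluable patients. The Clopper-Pearson lower limit is the 2.5% quantile of Beta(x, n − x + 1). With n = 35 and x = 0.58 × 35 = 20.3, it is 40.2%. With x = 0.72 × 35 = 25.2, it is 54.3%. Both reproduce. The 35 are patients who complete 8 weeks, so the planned precision belongs to the completer set and not to the FAS.

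**Step 2. Which denominator includes an early failure?** Take a patient stopped before Week 8 for progression.

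| Denominator | Source | Is the patient counted? |
|---|---|---|
| Week 8 healers | SAP 5.2, endpoint text | No |
| FTS, protocol definition | Protocol 9.2 | No |
| FTS, SAP definition | SAP 2.6.4 | Unclear: the patient attends a Visit 6 assessment on stopping |
| FAS, observed cases | SAP 5.2 opening; SAP 5.4 | In the set, but with no Visit 7 and no rule coding the result as No |

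No row counts the patient as a failure with certainty.

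**Step 3. Size of the early-stop effect.** The inputs are 35 completers (Protocol 9.1) and, as assumptions, 25 healed at Week 8 (25/35 = 71%, near the planned 72%) and 20 of those still healed at Week 32. Let k be the number of early failures; the documents give no value. The rate over all treated is 20/(35 + k).

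| k | Share of treated stopping early | Durable rate | Exact 95% CI |
|---|---|---|---|
| 0 (FTS) | 0% | 20/35 = 57.1% | 39.4 to 73.7 |
| 3 | 3/38 = 7.9% | 20/38 = 52.6% | 35.8 to 69.0 |
| 6 | 6/41 = 14.6% | 20/41 = 48.8% | 32.9 to 64.9 |
| 9 | 9/44 = 20.5% | 20/44 = 45.5% | 30.4 to 61.2 |

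The healer-subset rate is 20/25 = 80.0% (59.3 to 93.2) for every k. The gap depends on the assumed number of durable healers. At k = 9, 15 durable healers give 42.9% against 34.1% (8.8 points), and 25 give 71.4% against 56.8% (14.6 points).

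**Step 4. Deterioration in follow-up.** Keep 25 healers and 20 durable, so that 5 fail. Suppose that m of the 5 are discontinued for deterioration and have no value assigned to Visit 7. The observed-case healer rate becomes 20/(25 − m): 20/24 = 83% for m = 1, 20/22 = 91% for m = 3 and 20/20 = 100% for m = 5, against 80% when all five count as failures. SAP 2.5 assigns data to the nearest scheduled visit, so a late discontinuation assessment might be mapped to Visit 7. The loss is therefore possible, not certain.

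**The case against.** Several points on the other side stand.

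- **The loss is not hidden.** A reader might infer that replacement conceals early failures by holding the set at 35. The documents do not support that. SAP 2.6 and Table 14.1.1 give the size of each analysis set, and SAP 3.1 and Table 14.1.2 give disposition with reasons. Replaced patients stay in the FAS, so a careful reader can divide the durable healers by the FAS count. The durable-healing tables themselves will not show this.
- **The SAP is inconsistent rather than settled on completers.** The general FAS sentences in SAP 5.2 and 5.4 point the other way. It would be too strong to say that early failures can never count.
- **The completer reading is not certain under the SAP.** Visit 6 is also the premature discontinuation visit, and the SAP supersedes the protocol's statistical text. The protocol definition and the name of the set favour the completer reading.
- **The objective is narrower than the rationale.** Protocol 3.1 asks about patients who heal and remain healed, and the healer-subset rate answers that directly. The all-treated rate answers the question in Protocol 2.4.
- **Inflated Week 8 healing is not shown.** A reader might infer that an unmasked investigator could stop unhealed patients at Week 4 and so raise Week 8 healing among completers. The investigator criterion is no improvement from a Grade 3 baseline. A Grade 2 patient has improved, and the documents do not say how many would be unchanged. Week 8 epithelial healing also has FAS, LOCF and worst-observation tables.
- **Not every early stop is a known failure.** A patient who stops for an adverse event may be healed at the Visit 6 assessment. Counting that patient as No is a choice of estimand.
- **The study is descriptive.** SAP 2.10 calls it exploratory and hypothesis generating.

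None of this supplies a rule that counts a known failure without Visit 7.

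**Conclusion.** The concern holds for the two durable-healing rates. Their specific text and tables leave out an all-treated denominator, in conflict with the SAP's general sentences. Applying those sentences would still drop patients who have no Visit 7. On the protocol's FTS definition, known early failures do not count against durability. Week 8 healers who deteriorate later may also be lost.

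In the illustration, the planned 57% falls to between 53% and 45% with 3 to 9 early failures. This rests on assumed counts (35 completers, 20 durable healers, every early stop a failure); the real size depends on an early-stop rate that the documents do not give. The documents do not support extending the point to Week 8 healing, to concealment of the losses, or to a need to change the replacement rule. Replacement does no harm to a rate computed on the FAS with failures coded.

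The change should be made before database lock. It is a matter of reporting secondary results correctly and does not affect the primary analysis.

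**What to change.** 1. **Add the FAS as a denominator** for both durable-healing rates in SAP 5.2 and in Tables 14.2.1.2 and 14.2.2.2.
   - Code as No: patients not healed at Week 8, patients who stopped before Week 8 for progression or non-response, and Week 8 healers discontinued for deterioration during follow-up.
   - Also count as No in the FAS rate: other early stops and missing Visit 7 values (adverse event, withdrawn consent, loss to follow-up). Give an observed-case version as a sensitivity analysis, so that the effect of this choice is visible.
   - Keep the healer-subset and FTS rates as supportive.
2. **Reconcile the FTS definitions** in Protocol 9.2 and SAP 2.6.4, and state whether a patient whose Visit 6 is a premature discontinuation visit belongs to the set.
3. **Reconcile the timing of the non-response criteria** in the two Protocol 6.2 bullets and Protocol 3.3. Which clinical rule applies is for the sponsor to state.

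The cost is SAP wording, two extra table columns and a clarification of the protocol text. No patients or assessments are added. The FAS rate will be less favourable, and it will be conservative where the outcome is truly unknown.
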